## 5.1. Hypotheses and Decision Rules

This is a descriptive study, therefore there are no decision rules and statistical hypothesis testing to be performed. The objective of the study is to estimate safety and efficacy parameters, separately for each treatment arm.

## 5.2. General Methods

## 5.2.1. Analyses for Binary Endpoints

Binary endpoints (response based on IGA, EASI-75 and SCORAD75 and incidence of bone safety findings) will be presented using proportions together with the 95% confidence

PFIZER GENERAL BUSINESS

interval calculated using the normal approximation (or the Clopper-Pearson exact method when the estimated proportion is 0 or 1). Incidence of adverse events will be presented using frequency counts and percentages.

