3. OBJECTIVES, ENDPOINTS, AND ESTIMANDS

Objectives	Endpoints	Estimands	
Primary substudy objective(s):	Primary substudy endpoint (as secondary endpoints for B7451094):	Primary substudy estimand(s):	
• To evaluate the potential effects of abrocitinib on bone development in adolescent participants 12 to <18 years of age, as assessed by knee MRI.	• The proportion of bone safety findings in knee MRI 1 year after randomization in adolescent participants exposed to abrocitinib 100 mg and 200 mg QD.	• The primary substudy estimand is the incidence of bone safety findings in knee MRI after 1 year of being exposed to abrocitinib in adolescent participants 12 to <18 years of age, regardless of dosing compliance or treatment discontinuation.	

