10.10.10.1. Sample Size Determination

Adolescent participants 12 to <18 years of age in the main study will be eligible for enrollment into the substudy.

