10.10.10.3. Substudy Safety Analyses

Bone safety findings as adjudicated by the safety adjudication committee will be summarized by treatment group using frequency and proportions along with 95% CI for the proportions. Further details will be specified in the SAP.

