## PFIZER GENERAL BUSINESS

## 2.1.3. Additional Estimand(s)

The primary substudy estimand is the incidence of bone safety findings in knee MRI after 1 year of being exposed to abrocitinib in adolescent participants 12 to <18 years of age, regardless of dosing compliance or treatment discontinuation. This estimand is defined according to the primary substudy objective and is in alignment with the primary substudy endpoint. It includes the following 4 attributes:

- Population: Patients aged 12 to <18 years with moderate to severe AD, as defined by the substudy inclusion and exclusion criteria;
- Variable: Binary indicator of whether the participant had bone safety findings in knee MRI 1 year after randomization;
- Intercurrent event(s): Dosing compliance or treatment discontinuation is not considered for analysis. All data collected (including data after discontinuation of treatment) are included.
- Population-level summary: Incidence rate of bone safety findings, defined as the number of participants with bone safety findings in knee MRI 1 year after randomization divided by the number of participants that received treatment during the substudy, in each treatment arm.

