## PFIZER GENERAL BUSINESS

• The incidence rate of bone safety findings in knee MRI, along with the 95% CI will be estimated for baseline and End of Treatment (EOT) in the substudy, for each treatment arm. In addition, the types of bone safety findings will be summarized.

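### The SAP's interval for bone safety findings has a lower upper limit with one case than with none, at any arm size of 7 or more

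*SAP*

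**What the plan says.** Protocol 10.10.10.3 asks for adjudicated bone safety findings to be summarized by treatment group "using frequency and proportions along with 95% CI for the proportions" and leaves further detail to the SAP. SAP 5.2.1 supplies the method. It begins "Binary endpoints (response based on IGA, EASI-75 and SCORAD75 and incidence of bone safety findings) will be presented using proportions together with the 95% confidence" and says the interval is "calculated using the normal approximation (or the Clopper-Pearson exact method when the estimated proportion is 0 or 1".

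SAP 6.3.1 applies it: "The incidence rate of bone safety findings in knee MRI, along with the 95% CI will be estimated for baseline and End of Treatment", separately by arm. It names no other method, and SAP Appendix 1 asks only for point and interval estimation. The denominator, in SAP 2.1.3, is the number with findings "divided by the number of participants that received treatment during the substudy, in each treatment arm".

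Protocol 9.3.3 lets the analyst choose whichever of the two methods is appropriate, but only for the IGA, EASI-75 and SCORAD75 response rates. It does not reach the bone endpoint.

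The substudy section on sample size gives no number, only that "Adolescent participants 12 to <18 years of age in the main study will be eligible for enrollment into the substudy". Protocol Section 3 heads this endpoint "Primary substudy endpoint (as secondary endpoints for B7451094".

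**The concern.** The rule changes method between zero cases and one case. The Clopper-Pearson interval at zero is wide, as it should be when nothing has been seen. The Wald interval at one case is too short on the upper side, because its standard error comes from a very small estimated proportion. Joining the two can make the reported upper limit fall when a case is added, and the Wald lower limit can fall below zero.

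For a safety finding, the upper limit tells the reader which rates the data exclude. SAP 5.1 says "This is a descriptive study, therefore there are no decision rules and statistical hypothesis testing to be performed", so the interval is the only planned statement of uncertainty for the primary substudy endpoint. Low counts such as 0, 1 or 2 are where the rule behaves worst, and they are plausible for this endpoint.

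**Working it through.** **Inputs.** The method is from SAP 5.2.1 and the level is 95%. I take it as two-sided, with the plain Wald formula, because the SAP mentions no continuity correction. The number per arm is not stated, so the values of n below are assumptions. The ceiling is about 100, a whole main-study arm. No expected rate is given either.

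**The plan's own figure.** The only precision figure in the documents is for the main study: a maximum margin of 10% for any AE with 100 per arm (Protocol 9.5). The Wald half-width at a proportion of 0.5 is 1.96 × √(0.25/100) = 9.8%, so that figure is reproduced. None is given for the substudy.

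**Formulas.**
- Upper limit at 0/n (Clopper-Pearson): 1 − 0.025^(1/n).
- Limits at 1/n (Wald): 1/n ± 1.96 × √[(1/n)(1 − 1/n)/n].

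**Worked at n = 25.**
- 0/25: 1 − 0.025^(1/25) = 13.7%.
- 1/25: 0.04 ± 1.96 × √(0.04 × 0.96/25) = 0.04 ± 1.96 × 0.0392, which gives −3.7% to 11.7%.
- Clopper-Pearson at 1/25: 0.1% to 20.4%.

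| n per arm | Upper at 0 cases (exact) | Upper at 1 case (Wald) | Lower at 1 case (Wald) | Upper at 1 case (exact) |
|---|---|---|---|---|
| 6 | 45.9% | 46.5% | −13.2% | 64.1% |
| 7 | 41.0% | 40.2% | −11.6% | 57.9% |
| 20 | 16.8% | 14.6% | −4.6% | 24.9% |
| 25 | 13.7% | 11.7% | −3.7% | 20.4% |
| 40 | 8.8% | 7.3% | −2.3% | 13.2% |
| 50 | 7.1% | 5.9% | −1.9% | 10.6% |
| 100 | 3.6% | 3.0% | −1.0% | 5.4% |

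The upper limit falls at every n from 7 to 1000 and rises only for n = 2 to 6. It does not die out as n grows: n times the upper limit tends to −ln(0.025) = 3.69 at zero cases and to 1 + 1.96 = 2.96 at one case. With a continuity correction of 1/(2n), the fall would still occur, from n = 24.

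**What the one-case limit excludes.** A two-sided 95% upper limit should be the rate at which a count this low or lower has probability 2.5%. At n = 25 and a true rate of 11.7%, the probability of 0 or 1 case is 19.3%. At the exact limit of 20.4% it is 2.5%. The corresponding probabilities at the Wald limit are 19.0% for n = 20 and 19.9% for n = 50.

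**Coverage of the SAP rule (exact binomial sums).**
- True rates of 1% to 5%, n = 20 to 50: about 99.4% or higher. The rule does not under-cover there.
- True rates from just above the one-case Wald limit to 20%:

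| n per arm | Lowest | Mean | Highest | Mean chance that the upper limit is below the truth | Clopper-Pearson, lowest |
|---|---|---|---|---|---|
| 20 | 84.8% | 88.2% | 92.0% | 10.7% | 96.1% |
| 25 | 84.6% | 89.7% | 95.1% | 9.2% | 95.8% |
| 50 | 84.7% | 91.5% | 95.2% | 7.5% | 95.1% |

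Misses on the other side average about 1%. At n = 25, coverage drops from 99.6% at a true rate of 11% to 85.3% at 12%, because a count of one stops covering.

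**The case against.** The best case for leaving the rule alone concerns its weight. No test, decision rule or comparison of intervals is planned. The count and proportion stand beside the interval, findings are adjudicated, and potential findings in the central read go to the sponsor's safety group within 24 hours (Protocol 10.10.8.1). No case would be hidden, and a reader who sees 1/25 would not conclude that risk had fallen.

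The reversal is also a single step. At n = 25 the upper limits for 0, 1, 2 and 3 cases are 13.7%, 11.7%, 18.6% and 24.7%. The fall is about 2 points at n = 25, 1.2 at n = 50 and 0.7 at n = 100. Under-coverage starts only above the one-case limit, and the averages above use a window that begins there and ends at an arbitrary 20%. Protocol 2.3 describes the preclinical findings as pointing to a low risk, and at rates of a few percent the rule over-covers. Finally, Clopper-Pearson is not the only repair: a Wilson limit at 1/20 is 23.6%, which also exceeds the 16.8% at 0/20.

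All of this is correct, and it limits the point to reporting. It does not make the one-case limit right. The size of the fall understates the error: at 1/25 the Wald limit is 8.7 points below the exact one (20.4 − 11.7). The documents do not rule out higher rates, and the same rule applies to baseline MRI, where findings need not be rare.

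**Conclusion.** The concern holds and should be fixed. As written, the SAP will report a lower upper limit for one bone safety finding than for none at any arm size from 7 upward, together with a negative lower limit unless the sponsor truncates it, which the SAP does not mention. This part does not depend on a guessed sample size beyond 7 per arm. It assumes only a two-sided 95% interval and the plain Wald formula.

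The coverage loss does depend on unstated quantities. Coverage is about 85% at worst, and 88% to 92% on average, for assumed arms of 20 to 50 and true rates between the one-case limit and 20%. At true rates of 1% to 5% there is none. The consequence is misstated precision, mostly toward reassurance, for the primary substudy endpoint. Counts, proportions and study decisions are unaffected.

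**What to change.** In SAP 5.2.1, take bone safety findings out of the shared rule, and state in 5.2.1 and 6.3.1: *For incidence of bone safety findings the 95% CI will be the two-sided Clopper-Pearson interval at all counts, at baseline and EOT, in each arm.*

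The SAP already uses this method at 0 and 1, so nothing new is introduced. The upper limit then rises with the count (at n = 25, from 13.7% at zero cases to 20.4% at one) and the lower limit is never negative. The rule for the efficacy endpoints can stay. With 100 per arm and the Phase 3 rates in Protocol 2.2.2 (lowest 23.7%, IGA at 100 mg), counts near zero are not expected for IGA or EASI-75 in the full arms.

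The change is to SAP wording only, with no effect on data collection or sample size. The interval becomes wider and conservative: 20.3 points instead of 15.4 at 1/25.

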# 5.2.2. Analyses for Continuous Endpoints

Continuous endpoints will be summarized using descriptive statistics, including the number of non-missing observations, mean, SD, median, first and third quartiles, minimum and maximum values. Descriptive summaries of the observed values and change from baseline for each time point will be provided, for each treatment arm.

## 5.2.3. Analyses for Categorical Endpoints

Categorical endpoints will be summarized by frequency counts and percentages. Unless otherwise specified, the calculation of percentages will include the missing category. Therefore, counts of missing observations will be included in the denominator and presented as a separate category.

## 5.3. Methods to Manage Missing Data

For the analysis of efficacy endpoints using descriptive statistics, missing values will not be imputed. For the analysis of safety endpoints, the sponsor data standard rules for imputation according to Clinical Data Interchange Standards Consortium (CDISC) and Pfizer Standards (CaPS) will be applied.

## 6. ANALYSES AND SUMMARIES

## **6.1.** Primary Endpoint(s)

## 6.1.1. Incidence of AEs/SAEs

- Estimand strategy: Treatment policy (Section 2.1.1).
- Analysis set: Safety (Section 4).
- Analysis methodology: Descriptive statistics.
- Intercurrent events and missing data: All adverse event data collected will be analyzed regardless of dosing compliance or treatment discontinuation; missing values will not be imputed.
- The number and proportion of participants who had treatment emergent adverse events will be presented for each treatment arm. Treatment emergent adverse events will be summarized according to type, frequency, severity, seriousness and relationship to abrocitinib in each treatment arm.

#### PFIZER GENERAL BUSINESS

## 6.2. Secondary Endpoint(s)

#### 6.2.1. Response based on IGA Score

- Estimand strategy: Composite (Section 2.1.2).
- Analysis set: FAS (Section 4).
- Analysis methodology: Descriptive statistics and 95% CIs.
- Intercurrent events and missing data: Missing data due to participant discontinuing treatment or from the study for any reason are considered non-response. In addition, participants who required a rescue medication are considered non-responders.
- The response rate along with the 95% CI will be estimated for each treatment arm. In addition, summary of IGA scores for all scheduled time points will be presented for each treatment arm.

### 6.2.2. Response based on EASI-75

- Estimand strategy: Composite (Section 2.1.2).
- Analysis set: FAS (Section 4).
- Analysis methodology: Descriptive statistics and 95% CIs.
- Intercurrent events and missing data: Missing data due to participant discontinuing treatment or from the study for any reason are considered non-response. In addition, participants who required a rescue medication are considered non-responders.
- The response rate along with the 95% CI will be estimated for each treatment arm. In addition, summary of EASI scores for all scheduled time points will be presented for each treatment arm.

#### 6.2.3. Response based on SCORAD75

- Estimand strategy: Composite (Section 2.1.2).
- Analysis set: FAS (Section 4).
- Analysis methodology: Descriptive statistics and 95% CIs.
- Intercurrent events and missing data: Missing data due to participant discontinuing treatment or from the study for any reason are considered non-response. In addition, participants who required a rescue medication are considered non-responders.

#### PFIZER GENERAL BUSINESS

• The response rate along with the 95% CI will be estimated for each treatment arm. In addition, summary of SCORAD total scores for all scheduled time points will be presented for each treatment arm.

## 6.2.4. Change from baseline in POEM Score

- Estimand strategy: While on treatment (Section 2.1.2).
- Analysis set: FAS (Section 4).
- Analysis methodology: Descriptive statistics.
- Intercurrent events and missing data: Data collected after treatment discontinuation or use of rescue medication at any time during the treatment period will be censored; missing values will not be imputed.
- Summary statistics for observed value and change from baseline in POEM Score will be presented for all scheduled time points, for each treatment arm.

#### 6.2.5. Change from baseline in ADCT Score

- Estimand strategy: While on treatment (Section 2.1.2).
- Analysis set: FAS (Section 4).
- Analysis methodology: Descriptive statistics.
- Intercurrent events and missing data: Data collected after treatment discontinuation or use of rescue medication at any time during the treatment period will be censored; missing values will not be imputed.
- Summary statistics for observed value and change from baseline in ADCT Score will be presented for all scheduled time points, for each treatment arm.

## 6.3. Other Endpoint(s)

#### 6.3.1. Incidence of bone safety findings in knee MRI

- Estimand strategy: Treatment policy (Section 2.1.3).
- Analysis set: SAS (Section 4).
- Analysis methodology: Descriptive statistics and 95% CIs.
- Intercurrent events and missing data: All data collected will be analyzed regardless of dosing compliance or treatment discontinuation; missing values will not be imputed.

## PFIZER GENERAL BUSINESS

• The incidence rate of bone safety findings in knee MRI, along with the 95% CI will be estimated for baseline and End of Treatment (EOT) in the substudy, for each treatment arm. In addition, the types of bone safety findings will be summarized.

## 6.4. Subset Analyses

Summary statistics for the efficacy endpoints (Section 6.2) will be presented by subgroups according to whether the participants received monotherapy or combination therapy based on the permitted concomitant AD therapies in the protocol.

## 6.5. Baseline and Other Summaries and Analyses

## 6.5.1. Baseline Summaries

Demographic, baseline disesase characteristics, and medical history will be summarized by treatment arm according to CaPS.

## 6.5.2. Study Conduct and Participant Disposition

Participants' evaluation, disposition, and discontinuation will be summarized by treatment arm according to CaPS.

## 6.5.3. Study Treatment Exposure

A summary of dosing compliance by treatment arm will be provided. Dosing compliance will be calculated as the percent of the number of doses of study drug the participant took out of the expected total number of doses. Number and percent of participants with compliance of < 80 % and > 120% will be provided for each treatment arm.

The exposure to study drug (computed as last dosing date – first dosing date + 1) will be summarized by treatment arm and according to duration categories (<1 week,  $\geq$ 1 week to <4 weeks,  $\geq$ 4 weeks to < 8 weeks,  $\geq$ 8 weeks to < 10 weeks, and  $\geq$ 10 weeks).

## 6.5.4. Concomitant Medications and Nondrug Treatments

Prior drug and non-drug treatments, concomitant drug and non-drug treatments will be summarized for each treatment arm according to CaPS.

## 6.6. Safety Summaries and Analyses

All safety analyses will be performed on the Safety population. These will be presented in a tabular format and summarized descriptively for each treatment arm following Pfizer standards as appropriate.

## 6.6.1. Adverse Events

Medical Dictionary for Regulatory Activities (MedDRA) will be used to classify all AEs with respect to system organ class and preferred term. Summaries will include treatment

## PFIZER GENERAL BUSINESS

emergent AEs/SAEs, withdrawal from active treatment due to AEs, and serious infections, defined as any infection (viral, bacterial, and fungal) requiring hospitalization or parenteral antimicrobials or meets other criteria that require it to be classified as a serious adverse event.

Any AEs that occur after signing Informed Consent and before randomization and the first dose of study drug will be listed but not summarized.

# 6.6.2. Laboratory Data

Laboratory data will be listed and summarized according to CaPS. Laboratory parameters will be summarized descriptively at baseline, Week 4 and EOT visits, and will include the observed and change from baseline values.

## 6.6.3. Vital Signs

Vital signs will be summarized descriptively over time. Summaries will include the observed and change from baseline values. Height and weight will be summarized at baseline.

## 6.6.4. Electrocardiograms

ECG parameters will be summarized at baseline and EOT visits and will include the observed and change from baseline values.

## 7. INTERIM ANALYSES

## 7.1. Introduction

No formal interim analysis will be conducted for this study. As this is an open-label study, the sponsor may conduct reviews of the data during the course of the study for the purpose of safety assessment. Interim safety and efficacy data after approximately 50% of the total sample size has been randomized in the study will be prepared and summarized to support presentation of initial results to India Bureau of Health (BoH). Additional summaries of interim data, including MRI data may be prepared to support presentation of results to regulatory agencies.

## 7.2. Interim Analyses and Summaries

Data package to be provided to India BoH for presentation of initial results will include derived CDISC Study Data Tabulation Model (SDTM) datasets and data summaries that will include descriptive statistics of collected data on safety and efficacy parameters, as well as demographic and baseline characteristics.

#### PFIZER GENERAL BUSINESS

# **8. APPENDICES**

# **Appendix 1. Summary of Analyses**

Endpoint	Population	Data Inclusion and Rules for Handling Intercurrent Events and Missing Data	Analysis Method
Incidence of AEs/SAEs	Safety	All data collected will be included regardless of intercurrent events. Missing data will not be imputed.	Descriptive statistics
Response based on IGA Score	FAS	Missing data due to discontinuation of treatment or from the study or use of rescue medication will be considered as non-response.	Descriptive statistics; point and interval estimation
Response based on EASI-75	FAS	Missing data due to discontinuation of treatment or from the study or use of rescue medication will be considered as non-response.	Descriptive statistics; point and interval estimation
Response based on SCORAD75	FAS	Missing data due to discontinuation of treatment or from the study or use of rescue medication will be considered as non-response.	Descriptive statistics; point and interval estimation
Change from baseline in POEM Score	FAS	Data collected after treatment discontinuation or use of rescue medication will be censored. Missing data will not be imputed.	Descriptive statistics
Change from baseline in ADCT Score	FAS	Data collected after treatment discontinuation or use of rescue medication will be censored. Missing data will not be imputed.	Descriptive statistics

# PFIZER GENERAL BUSINESS

Incidence of bone safety findings in knee MRI	Substudy Analysis Set	All data collected will be included regardless of intercurrent events. Missing data will not be imputed.	Descriptive statistics; point and interval estimation
		l	

## **Appendix 2. Data Derivation Details**

### Appendix 2.1. Definition and Use of Visit Windows in Reporting

Visit Label	Target Day	Definition [Day window]
Baseline	Day 1 (Day of first	Last observation prior to and
	dose)	including day of first dose
Week 2	15	Days 2 to 22
Week 4	29	Days 23 to 43
Week 8	57	Days 44 to 71
Week 12	85	Days 72 to 99
Substudy EOT a	366	Days 353 to 380 or observation collected at Early Termination
Substudy Follow-up b	394	Days 381 to 408 or observation collected after Early Termination

Visit windows will be used for efficacy variables.

a. For MRI and HSS Pedi-FABS assessments in the Substudy

b. For HSS Pedi-FABS assessments in the Substudy

If two or more assessments fall into the same window, the assessment closest to the Target Day will be used. If two assessments are equally distant from the Target Day in absolute value, the later assessment will be used.

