10.10.2. Substudy Schedule of Activities

Substudy Visit Identifier	Substudy Screening	Substudy Randomization (Baseline)	Substudy Recurring Visit [Week 12 (Day 85 ±3 days), 24 (Day 169 ±7 days), 36 (Day 253 ±7 days)]	Substudy Early Termination/End of Treatment Visit	Substudy Follow-up Visit ^a
	Main Study Screening (Day -28)	Main Study Day 1	Main study [Weeks 2, 4, 8, 12] ^e	Main Study Day 1 + 365 days ± 14 days	ET/EOT + 28 days ±3 days
Informed consent/assent ^b	Х				
Dispense Study Intervention		Х	Х		
Study Intervention Administration		Х	Х	Х	
Study Intervention Accountability			Х	Х	
MRI procedure ^c	Х			Х	
Assess knees of participant for relevant history	Х				
Review Inclusion/Exclusion criteria for the substudy	х				
Monitor if any discontinuation criteria for substudy have been met or not	Х	Х	Х		
Urine Pregnancy Test (for WOCBP only)		Х	Х	Х	Х
Assess for adverse events ^d	Х	Х	Х	Х	Х
Vital Signs	Х	Х	Х	Х	Х

PFIZER CONFIDENTIAL

Page 100

Substudy Visit Identifier	Substudy Screening	Substudy Randomization (Baseline)	Substudy Recurring Visit [Week 12 (Day 85 ±3 days), 24 (Day 169 ±7 days), 36 (Day 253 ±7 days)]	Substudy Early Termination/End of Treatment Visit	Substudy Follow-up Visit ^a
	Main Study Screening (Day -28)	Main Study Day 1	Main study [Weeks 2, 4, 8, 12] ^e	Main Study Day 1 + 365 days ±14 days	ET/EOT + 28 days ± 3 days
Clinical Chemistry, Hematology (including coagulation panel), Lipid Profile ^f	Х		X ^f	Х	
Contraception check ^g	Х	Х	Х	Х	Х
PROs					
HSS Pedi-FABS (1 month recall)	Х	Х		Х	Х
HSS Pedi-FABS (1 year recall)	Х	Х		Х	Х

a. Substudy follow-up visit should occur approximately 28 days after the substudy early termination/end of treatment visit. Note: if any participant requires MRI following the early termination/end of treatment visit, the expectation is that the MRI would be arranged as soon as feasible and that the substudy follow up visit be conducted as close to the stated visit window as possible. It will not be considered a protocol deviation as long as the substudy follow up visit occurs no more than 14 days after the completion of the MRI in such cases.

b. Informed consent and assent (if applicable) for the substudy will be included in the main study ICD or assent. Participants who subsequently reach the age of majority during the study will be required to be reconsented as an adult.

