c. Participants who turn 18 years during the main study will only have baseline MRI. Participants who have completed 3 months of treatment in the main study and turn 18 years of age during the substudy will be required to attend an early termination visit with an MRI scan.

d. AEs and SAEs are recorded/reported as per Section 8.3.

e. Visits corresponding to main visits. Week 12 visit is End of treatment visit for main study. For substudy participants, activities will be performed as per the substudy schedule of activities.

f. Clinical chemistry includes: urea, sCr, sCysC (at Screening only), estimated creatinine clearance, AST, ALT, TBili, alkaline phosphatase. The lipid profile will include total cholesterol, LDL, VLDL, HDL, and triglycerides. Hematology includes: hemoglobin, WBC, neutrophils (%, absolute), lymphocytes (%, absolute), platelets, and coagulation panel (APTT, PT/INR). Laboratory tests with abnormal results may be repeated once during the screening period; the last value will be used to determine eligibility. Fasting lipid profile panel require at least an 8 hour fast. If possible, participants should comply with fasting requirements at those visits detailed above. For all adolescent participants for the substudy, laboratory tests will be performed at Screening, Week 4 and Week 12 as per the main study SoA, as well as at the ET/EOT visit of the substudy.

g. Review and record contraceptive method and results of pregnancy testing. Confirm that the participant is adhering to the contraception method(s) required in the protocol. Refer to Appendix 4 for contraceptive guidance.

Primary substudy objective(s):		Primary substudy endpoint (as secondary endpoints for B7451094):	
•	To evaluate the potential effects of abrocitinib on bone development in adolescent participants 12 to <18 years of age, as assessed by knee MRI.	•	The proportion of bone safety findings in knee MRI 1 year after randomization in adolescent participants exposed to abrocitinib 100 mg and 200 mg QD.

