10.10.10.2. Substudy Efficacy Analysis

There are no efficacy analyses planned for this substudy.

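### SAP Appendix 2.1 gives a protocol-compliant 1-year knee MRI on Day 352 or after Day 380 no end-of-treatment assignment

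*SAP*

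**What the plan says.** **SAP.** Appendix 2.1 has one post-baseline row that covers MRI: Substudy EOT, target Day 366, "Days 353 to 380 or observation collected at Early Termination". Footnote a applies it to MRI and HSS Pedi-FABS. The next row, Substudy Follow-up, target Day 394, reads "Days 381 to 408 or observation collected after Early Termination", and its footnote is "b. For HSS Pedi-FABS assessments in the Substudy". The table's scope sentence is "Visit windows will be used for efficacy variables". If several assessments share a window, the one nearest the target day is used. SAP 6.3.1 estimates the incidence of bone safety findings at baseline and EOT only. SAP 2.1.3 divides by all participants who received treatment during the substudy.

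**Protocol.** The Substudy Schedule of Activities (10.10.2) puts the EOT visit at "Main Study Day 1 + 365 days ± 14 days", marks the MRI there, and puts follow-up at "ET/EOT + 28 days ±3 days". Section 10.10.4 also places the second scan at the EOT visit. Section 10.10.7.2, however, lets the MRI be arranged within roughly a month of the early-termination or EOT visit. Section 10.10.7.3 provides for a scan that was not done after EOT to be done before the follow-up visit. For main-study withdrawals, 10.10.4 allows about a month after their end-of-treatment or early-termination visit. Section 10.10.10.2 states: "There are no efficacy analyses planned for this substudy".

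**The concern.** The SAP window is narrower than the protocol permits, on both sides. A participant can complete the year, be scanned in line with the protocol, and have a scan that belongs to no analysis visit. Because MRI is reported only at baseline and EOT, no other summary timepoint would pick it up.

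This bears on the substudy's primary endpoint, a bone-safety proportion in adolescents. The denominator is fixed by treatment received, not by having a windowed scan. A finding without an EOT assignment would therefore leave the numerator and nothing would leave the denominator, so the error runs towards fewer findings. The study is open-label and the sponsor may review MRI data while it runs (Protocol 9.4 and 10.10.10.4), so the assignment rule should be written down before results are seen.

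The scope sentence adds doubt. It speaks of efficacy variables, footnote a names MRI, and the substudy has no efficacy analysis.

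**Working it through.** **1. Reproduce the SAP's days.** Target: 1 + 365 = Day 366, as in the SAP. Follow-up target: 366 + 28 = Day 394, as in the SAP. EOT window by the protocol: 366 − 14 = Day 352 to 366 + 14 = Day 380, which is 29 days. The SAP has Days 353 to 380, which is 28 days. The upper end agrees; the lower end starts one day late.

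The likely origin is a table convention. The offsets are 353 − 366 = −13 and 380 − 366 = +14. Week 8 (44 to 71, target 57), Week 12 (72 to 99, target 85) and Substudy Follow-up (381 to 408, target 394) have the same offsets.

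**2. Latest scan day under Protocol 10.10.7.2.** I read the allowance as time after the visit and take a month as 28 to 31 days (assumption).

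| EOT visit | Latest scan (visit + 28 to 31) | Shortest delay that passes Day 380 |
|---|---|---|
| Day 352 | Day 380 to 383 | 29 days |
| Day 366 | Day 394 to 397 | 15 days |
| Day 380 | Day 408 to 411 | 1 day |

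A visit on target with a scan up to 14 days later stays inside the window. A visit on the last permitted day with a scan the next day does not.

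**3. Catch-up scans.** The follow-up visit nominally falls between 352 + 28 − 3 = Day 377 and 380 + 28 + 3 = Day 411. A made-up scan before that visit can therefore also fall after Day 380. Footnote a of the Substudy Schedule of Activities lets the follow-up visit move if the MRI is late.

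**4. The narrow reading.** If every scan is done at the EOT visit, only Day 352 is uncovered: 1 of 29 permitted days, or 3.4%.

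**5. Effect on the reported proportion.** Let p be the true proportion with a finding, c the completers' share of the denominator, and f the share of completers' scans outside Days 353 to 380. Assume that everyone treated is scanned, that early-termination scans count, and that findings are equally likely on scans inside and outside the window. If unwindowed scans are left out of EOT,

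reported incidence = p × (1 − c × f).

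This cannot exceed p. With every visit on Day 366 and delays of at most 14 days, f = 0 and nothing changes. On the narrow reading with visits spread evenly over the 29 days, f = 1/29 and, with c = 1, the result is p × 28/29 = 0.966p. For the wider reading I give no figure, because the documents give neither c nor the delays.

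The formula leaves out one separate group: "Participants who turn 18 years during the main study will only have baseline MRI". Those participants have no EOT scan to assign.

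**The case against.** A fair defence has four parts.

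- **No exclusion rule.** A reader might infer that every completer scan after Day 380 is thrown away. The documents do not support that. The SAP has no rule discarding observations outside a window, and assignment by nominal visit would be a natural programming choice. This stands: the defect is a missing assignment, not a proven exclusion. The SAP's statement that all collected data are analysed does not fill the gap, since it concerns compliance, discontinuation and intercurrent events and assigns no scan to EOT.
- **Early termination.** A reader might infer that early-termination scans done after the visit are shut out, because the SAP distinguishes observations at and after early termination and keeps MRI out of the second row. That is too strong. Protocol 10.10.2 and 10.10.7.2 treat the scan as part of that visit, and 10.10.4 calls a scan done within about a month of it the early-termination MRI. The SAP phrase is most likely a visit label, though its wording could be clearer.
- **Size.** A reader might assume delays spread over a full month and arrive at a large loss. The protocol asks for a scan needed after EOT to be arranged at the earliest feasible time, and two of its passages put the scan at the visit itself. No such figure can be supported.
- **Closeness to 1 year.** The endpoint is defined 1 year after randomization, so a narrow window is defensible in principle. It does not explain why Day 352 is left out, or why permitted later scans have no stated handling.

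**Conclusion.** The mismatch is certain as arithmetic: completer scans on Day 352 or after Day 380 can comply with the protocol and yet have no EOT assignment in the SAP. The downward effect on the substudy's primary incidence is conditional on footnote a being applied literally. Its size is unknown. It is confined to one day if scans are done at the EOT visit, and larger if the allowance in 10.10.7.2 or the catch-up provision in 10.10.7.3 is used.

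A reader might also fear that bone findings would go unseen. They would not. Under Protocol 10.10.8.1, post-dose findings are adjudicated and recorded, and potential bone safety findings on the central read are reported to the sponsor's safety group within 24 hours, whatever the window. Those recorded as treatment-emergent events also enter the substudy adverse-event summary (SAP 5). What is at stake is one descriptive proportion with no hypothesis test attached. It is nevertheless the substudy's primary result, and the SAP should be corrected.

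**What to change.** In SAP Appendix 2.1:

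- Give MRI its own row. Assign to EOT, by nominal visit, the first post-dose MRI linked to the substudy EOT or early-termination visit. Start at Day 352 for completers, and include a catch-up MRI done because the EOT scan was missed.
- Set the end of the row at the participant's follow-up visit: the substudy follow-up visit, or the main-study end-of-study visit for main-study withdrawals.
- Word the early-termination part so that it covers a scan done within about a month of that visit.
- State that the nearest-to-target-day rule does not apply to MRI, so that a repeat scan prompted by a finding does not replace the first one.
- Amend the scope sentence to name MRI and HSS Pedi-FABS.
- List actual scan days.

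At the next protocol amendment, reconcile the Substudy Schedule of Activities and 10.10.4 with 10.10.7.2 on when the MRI is done. The SAP change does not depend on this.

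**Cost.** One table row, a few sentences and a listing; no new data. The protocol reconciliation needs IRB/EC approval (Protocol 10.1.1), which is why it can wait. The small downside is a wider spread of scan timing around 1 year, which the listing makes visible.
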